### **5.4 Concomitant Therapies**

#### **5.4.1 Concomitant Medication(s)**

Concomitant medications must be locally-approved and used at doses and regimens that are considered standard-of-care for the treated indication.

Treatment for co-morbidities, disease signs and symptoms and treatment emergent adverse events should be provided as necessary in the judgment of the investigator. Antibiotics and analgesics should be used as needed. Patients with neutropenic fever or infection should be treated promptly. Therapeutic colony-stimulating factors should be used in accordance with ASCO guidelines. Packed red blood cell and platelet transfusions may be administered as clinically indicated.

##### **5.4.1.1 Permitted Concomitant Medications**

Supportive Care/Palliative Care: Supportive and palliative care for disease related symptoms may be administered at the investigator's discretion, including the use of analgesics.

Anti-emetics: Patients may be premedicated for nausea and vomiting. Recommended anti-emetic agents include granisetron 1 mg as premedication, and then granisetron and/or prochlorperazine as needed.

Transfusions: Patients may receive transfusions as necessary.

##### **5.4.1.2 Cautioned Concomitant Medications and Substances**

P450 Considerations: Caution should be used when mocetinostat is administered to patients taking medications metabolized by CYP2C9, or that inhibit or induce metabolism by CYP2E1 or CYP3A4. See [Appendix 3](#) for examples of medications of interest. If a patient is taking a drug on one these lists, it is encouraged to substitute a different medication if possible.

Anti-Coagulation: At the discretion of the investigator and under medical supervision, patients may continue to receive prophylactic or therapeutic low molecular weight heparin (but not therapeutic treatment with warfarin, other coumarin derivatives) as clinically indicated.

#### 5.4.1.3 *Concomitant Medications and Substances to be Avoided On-Study*

Warfarin or Coumarin Derivatives: Therapeutic doses of warfarin or other coumarin derivative anticoagulants are not permitted. Warfarin has a narrow therapeutic range and mocetinostat can have inhibitory effects on CYP2C9, the main metabolizing enzyme of warfarin.

Drugs with QTc Prolonging Activity: As listed in [Appendix 3](#). This list is not exhaustive. Any questions should be discussed with the Sponsor.

Herbal Medications/Preparations: Herbal medications and preparations are not allowed throughout the study, as a potential drug-drug interaction is always possible. These herbal medications include, but are not limited to: St. John's wort, Kava, ephedra (ma huang), ginkgo biloba, dehydroepiandrosterone (DHEA), yohimbe (yohimbine), saw palmetto, and ginseng. Patients should stop using these herbal medications at least 7 days prior to first dose of study treatment.

Gastric Acid Neutralizers: Medications that directly increase gastric pH such as short-acting antacids should be avoided 4 hours before and 2 hours after administration of mocetinostat. Medications that affect gastric acid secretion, such as H2 antagonists or proton pump inhibitors should be avoided.

Contraceptives: Hormonal contraceptives may be affected by cytochrome P450 interactions, and are therefore not considered effective for this study, since induction of CYP3A4 may not be excluded in patients receiving mocetinostat.

Immunosuppressive Medications: Including, but not limited to systemic corticosteroids at doses not exceeding 10 mg/day of prednisone or equivalent, methotrexate, azathioprine, and TNF- $\alpha$  blockers. Use of immunosuppressive medications for the management of investigational product-related AEs or in patients with contrast allergies is acceptable. In addition, use of inhaled and intranasal corticosteroids is permitted. A temporary period of steroids will be allowed for different indications, at the discretion of the principal investigator (e.g., chronic obstructive pulmonary disease, radiation, nausea, etc).

Vaccines: Live attenuated vaccines within 30 days of durvalumab dosing are to be avoided (i.e., 30 days prior to the first dose, during treatment with durvalumab and for 30 days post discontinuation of durvalumab). Inactivated vaccines, such as the injectable influenza vaccine, are permitted.

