The percent of tumor cells expressing PD-L1 is predictive for responsiveness to treatment with durvalumab (Rebelatto-2015). The recommended threshold for positivity is  $\geq 25\%$  of tumor cells demonstrating membrane staining for PD-L1 at any intensity. Among patients with NSCLC, the ORR for cases positive for PD-L1 was 27% (23 of 84; 95% Confidence Interval [CI] 18.2-38.2%) as compared to 5% (5 of 92; 95% CI 1.8-12.2%) for cases negative for PD-L1 expression (Rizvi-2015). Subset analysis by histological classification shows the following disease response rates:

Histology	All Patients	PD-L1 +	PD-L1 -
Squamous	18/88 (21%)	14/43 (33%)	3/37 (8%)
Non-squamous	14/122 (13%)	9/41 (22%)	2/55 (4%)

In this study, the treatment regimen will begin with a 7-Day Lead-In Period of mocetinostat followed by start of the combination regimen of mocetinostat and durvalumab. The Recommended Phase 2 Dose (RP2D) of mocetinostat will be established in the Phase 1 dose escalation segment, followed by evaluation of the clinical activity of the combination regimen in patients having NSCLC.

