#### 4.2 Exclusion Criteria

Patients presenting with any of the following will not be included in the study:

1. Prior therapies:
  - a. All Cohorts
    - i. HDAC inhibitor for the treatment of the malignancy under study
    - ii. Immunotherapies not previously specified, including anti-CTLA-4, anti-OX40 and anti-CD137
  - b. Phase 2 Cohorts 1 and 2 – prior treatment with anti-PD-1 or anti-PD-L1
  - c. Phase 2 Cohorts 3 and 4 – receipt of systemic cancer treatments since progression of disease during or following administered checkpoint inhibitor
2. Patients with any history of tumors that test positive for *EGFR*, *ROS1*, *ALK* mutations or *ALK* fusions or any other mutations for which there are tyrosine kinase inhibitors available or under development.
3. Most recent prior therapeutic regimen discontinued  $\leq 3$  weeks before first study treatment dose date (i.e., mocetinostat Lead-in Period).

4. Lack of recovery from the adverse effects of prior therapy at the time of enrollment to  $\leq$  Grade 1 (excluding alopecia or neuropathy).
5. Previous treatment-related, severe ( $\geq$  Grade 3) AE or any neurologic or ocular AE of any grade while receiving checkpoint inhibitors. **NOTE:** Patients with a prior endocrine AE are permitted to enroll if they are stably maintained on appropriate replacement therapy and are asymptomatic.
6. Active or prior documented autoimmune disease within the past 2 years.  
NOTE: Patients with vitiligo, Grave's disease, or psoriasis not requiring systemic treatment (within the past 2 years) are not excluded.
7. Active or prior documented inflammatory bowel disease (e.g., Crohn's disease, ulcerative colitis).
8. Current or prior use of immunosuppressive medication within 28 days before the first dose of durvalumab, with the exceptions of intranasal and inhaled corticosteroids or systemic corticosteroids at physiological doses, which are not to exceed 10 mg/day of prednisone, or an equivalent corticosteroid.
9. Receipt of live attenuated vaccination within 30 days prior to study entry or within 30 days of receiving durvalumab.
10. History of primary immunodeficiency.
11. Known history of previous clinical diagnosis of tuberculosis.
12. Known history of acute or chronic hepatitis B, human immunodeficiency virus (HIV), or acute hepatitis C.
13. History of allogeneic organ transplant.
14. History of hypersensitivity to durvalumab, mocetinostat or any drug product excipient.

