15. History of interstitial lung disease (ILD), drug-induced ILD, radiation pneumonitis which required steroid treatment, or any evidence of clinically active interstitial lung disease.
16. History of stroke or transient ischemic attack within the previous 6 months.
17. Any of the following cardiac abnormalities:
  - a. Unstable angina pectoris,
  - b. Congestive heart failure  $\geq$  NYHA Class 3,

- c. QTc  $\geq$ 470 milliseconds on electrocardiogram (ECG) calculated using Frediricia's Correction, or
  - d. Current or history of a small, moderate or large pericardial effusion, and/or hemodynamic compromise due to pericardial effusion of any size. Minimal or trivial pericardial effusion is not excluded.
18. Concomitant medication known to cause prolonged QT which cannot be discontinued or changed to a different medication prior to enrollment.
19. Active brain metastases. Subjects are eligible if brain metastases are adequately treated and subjects are neurologically stable (except for residual signs or symptoms related to the CNS treatment) for at least 2 weeks prior to enrollment without the use of corticosteroids, or on a stable or decreasing dose of  $\leq$  10 mg daily prednisone (or equivalent).
20. Known or suspected presence of another malignancy that could be mistaken for the malignancy under study during disease assessments.
21. Pregnancy. WOCBP must have a negative serum or urine pregnancy test documented within the screening period prior start of study drug.
22. Breast-feeding or planning to breast feed during the study or within 6 months after study treatment.
23. Any psychiatric illness/social situations that would limit compliance with study requirements or compromise the ability of the patient to give written informed consent.
24. Any serious illness, uncontrolled inter-current illness, active or uncontrolled infection, or other medical history, including laboratory results, which, in the Investigator's opinion, would be likely to interfere with the patient's participation in the study, or with the interpretation of the results.

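### Section 5.4.1.3 tells sites to avoid systemic corticosteroids at or below 10 mg/day prednisone, the doses on which exclusions 8 and 19 knowingly admit patients

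*Protocol*

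**What the plan says.** Section 5.4.1.3 of the protocol is headed as a list of medications and substances to avoid on study. Under immunosuppressive medications it gives "Including, but not limited to systemic corticosteroids at doses not exceeding 10 mg/day of prednisone or equivalent", followed by methotrexate, azathioprine and TNF-α blockers. It then relaxes the rule for product-related adverse events, contrast allergy, inhaled or intranasal corticosteroids, and a temporary period of steroids at the principal investigator's discretion.

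The entry criteria in Section 4.2 treat the same doses differently:

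- Exclusion 8 bars "Current or prior use of immunosuppressive medication within 28 days before the first dose of durvalumab", but excepts "systemic corticosteroids at physiological doses, which are not to exceed 10 mg/day of prednisone" or equivalent.
- Exclusion 19 admits patients with adequately treated brain metastases who have been neurologically stable "for at least 2 weeks prior to enrollment without the use of corticosteroids, or on a stable or decreasing dose of" at most "10 mg daily prednisone (or equivalent").
- The note to exclusion 5 says: "Patients with a prior endocrine AE are permitted to enroll if they are stably maintained on appropriate replacement therapy". It names no drug and no dose.

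Table 9 and Appendix 4, on managing durvalumab immune-related events, also treat 10 mg/day or less as the acceptable range.

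**The concern.** A dose that is acceptable at entry appears by name among the drugs to avoid once the patient is on study. A site reading 5.4.1.3 literally would try to avoid continuing physiological or stable low-dose prednisone in a patient whom the protocol admitted on it. Where that steroid is hormone replacement, this is a question of patient care. Sites could also apply the rule differently from one another. SAP Section 9.2 has a prohibited-medication category for deviations, so continuing use might be logged there, although neither document says that it would be.

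**Working it through.** There is no planned figure to reproduce. The check is the direction of the dose threshold wherever the current text uses 10 mg/day of prednisone.

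**Step 1. Side by side.**

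| Place | Dose range named | Status of that range |
|---|---|---|
| Protocol 5.4.1.3 | ≤ 10 mg/day | to be avoided on study |
| Exclusion 8 | ≤ 10 mg/day | excepted from exclusion |
| Exclusion 19 | ≤ 10 mg/day, stable or decreasing | eligible |
| Table 9, permanent discontinuation | ≤ 10 mg/day | must be reached within 12 weeks of the last dose, or durvalumab stops |
| Table 9, Grade 2 endocrinopathy | ≤ 10 mg/day | retreatment allowed |
| Appendix 4, Grade 2 endocrinopathy | ≤ 10 mg/day | retreatment allowed |

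Section 5.4.1.3 is the only entry pointing the other way. The phrase is an item in the list of avoided drugs, so it cannot be read as an exception to that list.

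**Step 2. Which of these conflict in operation.** Exclusions 8 and 19 do: 2 direct conflicts. The three adverse-event statements (two distinct rules, since the last two rows repeat one rule) fall under 5.4.1.3's own exception for product-related events. They show the intended direction and add 0 operational conflicts.

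The exclusion 5 note adds 1 conditional conflict. Section 1.3.3 counts adrenal insufficiency and hypophysitis among the endocrinopathies, and Appendix 4 names hydrocortisone as a replacement hormone. Replacement therapy could therefore be a steroid. Such an event would have arisen on an earlier checkpoint inhibitor, so the exception for product-related events would not ordinarily cover it.

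**Step 3. Do the exceptions cover what remains?** Adverse-event management, contrast allergy, inhaled or intranasal use and temporary use do not cover a stable systemic dose carried on from entry. A decreasing dose under exclusion 19 may count as temporary, so the affected use is stable and continuing.

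**Step 4. Can an entry rule and an on-study rule be kept apart?** Not fully. The exclusion 8 window is anchored to the first durvalumab dose. Section 1.5 puts a "7-Day Lead-In Period of mocetinostat followed by start of the combination regimen of mocetinostat and durvalumab", and exclusion 3 treats the Lead-in as the "first study treatment dose date (i.e., mocetinostat Lead-in Period").

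- Window: C1D1 − 28 to C1D1 − 1 = 28 days.
- Lead-in: C1D1 − 7 to C1D1 − 1 = 7 days.
- Overlap: 7/28 = 25% of the window.

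During those 7 days the same dose is acceptable under exclusion 8 and to be avoided under 5.4.1.3. This locates the overlap; it does not measure harm. Nor does any provision tell sites to stop or taper a low-dose steroid at enrollment, whereas for herbal products 5.4.1.3 does say when to stop (at least 7 days before first dose).

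**Step 5. Does the slip permit high doses?** No. The entry is expressly not exhaustive, so doses above 10 mg/day remain immunosuppressive medication to be avoided.

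**The case against.** The strongest reply is that this is an editorial slip whose intended meaning is clear from the rest of the protocol, with little practical effect. Section 5.4.1, the parent section, leaves treatment of comorbidities and symptoms to the investigator's judgment. The restriction is also mild: warfarin and herbal products are barred outright in the same section, while immunosuppressives are only under a heading of things to avoid, with several relaxations. Exclusions 8 and 19 are entry criteria, and admitting a patient on a drug while preferring that it be avoided afterwards is odd but not strictly contradictory. The exclusion 5 note names no steroid. Whether a deviation would count as important depends on a separate guidance document that is not among the documents reviewed.

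Much of this limits the weight of the point. The affected group is narrow and uncounted, the exclusion 5 conflict is conditional, the deviation consequence is only possible, and the 25% overlap says nothing about how many patients are affected. It does not remove the inversion. A general supportive-care provision does not override an item named specifically in the avoid list. No exception covers stable continuing low-dose use, and the Lead-in overlap prevents a clean split between entry and on-study rules. The error is in an operative conduct rule that sites follow.

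**Conclusion.** The concern holds: the threshold in Section 5.4.1.3 is inverted and should be corrected. It conflicts directly with 2 entry criteria (exclusions 8 and 19) and conditionally with 1 more (the exclusion 5 note, if the replacement is a steroid). The practical reach is stable, continuing systemic use at or below 10 mg/day outside the listed exceptions; the number of such patients cannot be derived from the documents. The consequence concerns conduct and patient care, with no effect on sample size, error rates, analysis populations or efficacy analyses. The conclusion rests on reading 5.4.1.3 as printed and on taking the intended direction from exclusions 8 and 19, Table 9 and Appendix 4, which all agree.

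**What to change.** In Section 5.4.1.3, change the corticosteroid item so that it names doses exceeding 10 mg/day of prednisone or equivalent, and leave the existing exceptions as they are. This resolves both direct conflicts, and the exclusion 5 one where the replacement dose is at or below 10 mg/day. In deviation review, do not count continuing use at or below 10 mg/day as prohibited medication. The cost is one phrase in an amendment or administrative letter, both of which Section 13.1 provides for, with the usual ethics submission. No SAP analysis needs to change.

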#### **5.4.2 Concomitant Surgery or Radiation Therapy**

The use of surgery to manage cancer lesions during study treatment is discouraged. The impact of treatment with mocetinostat on wound healing has not yet been characterized. For patients with bone involvement, any foreseeable need for palliative radiotherapy should be addressed before study entry, if possible and clinically appropriate (e.g., bone lesions at risk for spontaneous micro-fractures or painful lesions). However, these treatments may be used in cases where it is medically necessary.

#### **5.4.3 Other Anticancer or Experimental Therapy**

Use of approved or investigational anticancer treatment will not be permitted during the study treatment period, including chemotherapy, biological response modifiers, hormone therapies or immunotherapy. No other investigational drug may be used during treatment on this protocol. Concurrent participation in another therapeutic clinical trial is not allowed.

## **6 STUDY ASSESSMENTS**

### **6.1 Screening**

Voluntary, written, dated, and signed informed consent must be obtained before any study specific procedures are performed. Patients who completed the informed consent process but did not enroll on the study will be considered as screen failures. Limited information will be recorded in the CRF for these patients.

### **6.2 Study Period**

For details on procedures during the study period, see Schedule of Assessments as shown in [Table 1](#) and [Table 2](#).

### **6.3 End of Treatment Assessment**

All patients will be followed for AEs for at least 28 days and for SAEs for at least 90 days following the last dose of Study Treatment. See the Schedule of Assessments ([Table 1](#)) for evaluations to be performed at the End of Treatment visit.

### **6.4 Long-Term Follow-up and End of Study Assessment**

Blood samples for MEDI4736 PK and ADA will be collected approximately 90 days after the last infusion of durvalumab. Survival status and subsequent therapies will be collected during long term follow-up as outlined in the Schedule of Assessments ([Table 1](#)) until death or lost to follow-up. Beyond 90 days after last treatment, follow-up

may be performed by telephone contact. Treatments received following participation in the study will be collected in the CRF.

## **6.5 Patient Discontinuation/Withdrawal**

Patients may discontinue from study treatment or from the study at any time at their own request, or they may be discontinued at any time at the discretion of the investigator or Sponsor for safety, behavioral reasons, or the inability of the patient to comply with the protocol required schedule of study visits or procedures at a given study site.

Criteria that may be used to discontinue patients from receipt of study medication will include, but will not be limited to:

- Objective disease progression according to RECIST 1.1 as determined by the investigator (patients who may derive clinical benefit may continue on treatment at the discretion of the investigator);
- Global deterioration of health status requiring discontinuation;
- Adverse event;
- Significant protocol violation;
- Lost to follow-up;
- Refusal for further treatment;
- Study termination by Sponsor;
- Death.

Reasons for discontinuation from study follow-up may include:

- Study terminated by Sponsor;
- Lost to follow-up;
- Refusal for further follow-up for survival;
- Death.

If a patient does not return for a scheduled visit, every effort should be made to contact the patient. At least 2 attempts should be made to contact the patient, and each attempt should be recorded in the source documents. In any circumstance, every effort should be made to document patient outcome, if possible. The investigator should inquire about the

reason for withdrawal, request that the patient returns for a final visit, and if applicable, follow-up with the patient regarding any unresolved adverse events.

If the patient withdraws from the study treatment and also withdraws consent for disclosure of future information, no further evaluations should be performed, and no additional data should be collected. The Sponsor may retain and continue to use any data collected before such refusal for further follow-up.

## **7 PROCEDURES**

Every effort should be made to ensure that the protocol required tests and procedures are completed as described. However it is anticipated that there may be circumstances outside of the control of the investigator that may make it unfeasible to perform a protocol-specified assessment. In these cases the investigator will take all steps necessary to ensure the safety and well-being of the patient. When a protocol required test cannot be performed, the investigator will document in the source document and CRF the reason and any corrective and preventive actions which he/she has taken to ensure that normal processes are adhered to as soon as possible. The study team will be informed of these incidents in a timely fashion.

### **7.1 Sample Collection for PD-L1 Expression**

Tumor tissue testing for PD-L1 expression is required for patients enrolling in Phase 2 Cohorts 1 and 2 and encouraged for patients enrolling in the Phase 1 study or Phase 2 Cohorts 3 and 4. In Cohorts 1 and 2, the sample tested must have been collected following completion of the most recent systemic treatment regimen. In other patient cohorts, when the collection of a new sample is not clinically appropriate, archival samples may be utilized provided the specimen it is not older than 3 years of age.

Samples should be collected via a core needle of 18 gauge or larger or be collected by an incisional or excisional tumor biopsy. Where institutional practice uses a smaller gauge needle, samples should be evaluated for tumor cell quantity (i.e., > 100 tumor cells) to allow for adequate PD-L1 immunohistochemistry analyses.

Samples submitted for PD-L1 testing should be formalin fixed and embedded in paraffin. Samples from fine needle aspirates (FNA) or decalcified bone are not appropriate for PD-L1 analysis.

Further guidance on sample preparation and submission can be found in the Study Laboratory Manual.

